c. The principal investigator, [name], is responsible for monitoring the data, assuring protocol compliance, and conducting monthly safety reviews. During the review process the principal investigator will evaluate whether the study should continue unchanged, require modification/amendment, or close to enrollment.

The principal investigator or the Institutional Review Board (IRB) have the authority to stop or suspend the study or require modifications.

This protocol presents minimal risks to the participants and Unanticipated Problems Involving Risks to Participants or Others (UPIRSOs), including adverse events, are not anticipated. In the unlikely event that such events occur, Reportable Events (which are events that are serious or life-threatening and unanticipated (or anticipated but occurring with a greater frequency than expected) and possibly, probably, or definitely related) or Unanticipated Problems Involving Risks to Participants or Others that may require a temporary or permanent interruption of study activities will be reported immediately (if possible), followed by a written report within 5 calendar days of the Principal Investigator becoming aware of the event to the IRB (using the appropriate forms from the website) and any appropriate funding and regulatory agencies. The investigator will apprise fellow investigators and study personnel of all UPIRSOs and adverse events that occur during the conduct of this research project through regular study meetings and via email or telephone. The protocol’s study sponsors, funding and regulatory agencies, and regulatory and decision-making bodies will be informed of serious adverse events within 5 days of the event becoming known to the principal investigator.

13. **Statistical Considerations:** *Describe the statistical analyses that support the study design.*

R61 Statistical Power: Aims 1-3: Since all participants will perform all studies in Aims 1-3 (Conditioned Hallucinations, Social Learning and Linguistic Markers), we powered our study based on our own preliminary data. Estimated effects for our proposed study of the impact of SING on conditioned hallucinations model parameters are based upon our own data in **Figure 2**. If SING can curtail these group differences – i.e. decrease hallucinating patient responses to the level of non-hallucinating controls, then we would predict the true difference in HGF model parameters pre- versus post-SING would be 0.01 arbitrary units and the within-patient standard deviation of the parameter estimates would be 0.02. We will analyze the model parameter specific to each Aim using paired sample's t-tests, leveraging the added power of within-participant designs. We estimate we will need at least 31 participants to have 80% power to detect a treatment difference at a two-sided 0.05 significance level⁵⁴. We budgeted for 50 unique participants to allow for participant drop-out and the detection of smaller effects of SING on conditioned hallucination behavior, social learning and language use.

Go/No Go Decision: We powered the R61 phase in order to detect complete resolution of conditioned hallucination metrics to the level of non-hallucinating control participants. But we propose a much larger sample of participants in order to be powered to detect smaller changes in conditioned hallucination metrics, social learning and language use. Given standard pharmacotherapies for hallucinations are associated with residual symptoms in 30-50% of participants⁵⁵, it would seem an unfairly high bar to demand complete normalization of a candidate behavioral metric in order for an effect on that metric to be meaningful and solicitous of follow-up investigation. In the clinical trials literature, Jacobson and Truax⁵⁶ determining clinical significance is often used. It is defined as two standard deviations or greater change in the direction of symptomatic improvement following treatment. We propose to adopt this standard for each metric examined in each of Aims 1-3. **Conditioned Hallucination parameters, social learning rates or use of personal pronouns, biological words or negative emotional words change by two standard deviations or more from baseline pre-intervention, then those metrics will proceed to our R33 study. If no metrics meet that standard, we will not proceed with the R33.**

		ACTIVE	
		-	+
OWNERSHIP	-	Listening (pop music) n=50	Karaoke (no recording) n=50
	+	Listening (curated playlists) n=50	SING (producing, performing) n=50

Figure 6. R33 Design

R33 Phase: Should we demonstrate a meaningful impact of SING on computational metrics of behavior, we will proceed to use those metrics in the R33 phase where we aim to deconstruct the active ingredients of SING along two key dimensions, Activity (whether engagement with the group is active or passive) and Ownership (creating some novel musical product, or not). Following screening, once participants have been deemed eligible, their behavior on the selected behavioral metrics will be assayed and they will be randomized to an intervention group. Performance on our computational metrics will be balanced across intervention groups prior to commencement of the four interventions (total n=200, n=50 per intervention, 10 groups of 5 participants per intervention):

- (1) **Passive Listening without Ownership** (Activity - / Ownership -, n=50). The group will meet on four occasions, once a week for two hours. The trained facilitator, having procured a playlist of popular music, will spend 15 minutes introducing the session, reminding participants not to sing along and to just sit quietly listening to the music. Next, the facilitator will play music from the playlist through a high-quality speaker at 60-75 decibels for 90 minutes. In the final 15 minutes, the facilitator will summarize the session and dismiss the participants, sharing follow-up music opportunities at the end of the fourth and final session.

- (2) **Passive Listening with Ownership** (Activity - / Ownership +, n=50). The trained facilitator will provide a computer and speaker with the ability to stream songs through many media outlets (i.e., Spotify, YouTube, Google). In the first fifteen minutes, the facilitator will introduce the session, participants are reminded not to sing along and to just sit quietly listening to the music. Next the participants will choose songs that they would like to hear. The list can be edited at any point. For the next 90 mins, the playlist will be played through a high-quality speaker at 60-75 decibels. In the final 15 minutes, the group will be concluded, and the participants will be dismissed. If it is the final session, they will be offered follow-up information about the musical opportunities.
- (3) **Karaoke** (Activity +/ Ownership -, n=50). The trained facilitator will provide a microphone and speaker along with a karaoke playlist of music and a screen to view lyrics. In the first 10 minutes, participants will be encouraged to write down a list of songs that they would like to sing to. The list can be edited at any point. For 5 minutes, they will conduct body and vocal warm ups, listening to self and others. For 90 minutes, the facilitator will order the participants in turn and invite them to perform karaoke at 60-75 decibels. Each participant will be encouraged to participate. For the final 15 minutes, the session will be concluded, and if the final session, participants will be informed of local opportunities to engage further with music making and musical experiences.

[figure not shown]

Figure 7. Behavioral simulation across three iterations of the HGF. 1) (top panel) standard HGF implementation; 2) (middle panel) adding Nu, which codes the weighting between sensory evidence and perceptual beliefs; 3) (bottom panel) allowing a more flexible influence of Nu on the overall model. Simulated responses were then compared with observed behavior, comparing the proportion of identical responses (left), individual phi coefficients (middle), and proportion of “yes” responses (right).

- (4) **SING** (Activity +/- Ownership +, n=50). As in the R61, the trained facilitator will provide a keyboard, professional microphone, recording interface, headphones, guitar, computer and a Digital Audio Workstation (DAW) for recording. The first 10 minutes of group involve introductions to the other participants and facilitator as well as the goals of the session. Participants will be given paper and a pencil with which to brainstorm potential lyrics. The next 5 minutes involve body and vocal warm ups, listening to self and others. For the next 90 minutes, participants will work together with the facilitator and independently to create their own original lyrics and melody. Each song will have at least one collaborative section (usually the chorus) where lyrics are written and performed together by the whole group. Participants also can write alone and perform sections by themselves. For the last 10 minutes, the group listens back to the entire song that they created. In the final 5 mins, the session is concluded, and the group disbands until the next session. If it is the final session, information sheets on local studio opportunities, karaoke nights and other opportunities to produce, perform and experience music.

For all four intervention types, at the end of each session, the facilitator notes level of contribution and any other significant points regarding individual participation and group coherence (these may be used to weight each participant's contributions to analyses of the intervention's impact on computational behavioral endpoints

R33 Power to Detect Effects. Since all participants will perform all tasks; Conditioned Hallucinations, Social Learning and Linguistic Markers, we powered the R33 based on our own preliminary data (on the understanding that any and all of the tasks from the three R61 aims may or may not progress to the R33). Estimated effects for our proposed study of the impact of SING on conditioned hallucinations model parameters are based upon our own data in **Figure 2**. If SING can curtail these group differences – i.e. decrease hallucinating patient responses to the level of non-hallucinating controls, then we would predict the true difference in HGF model parameters pre- versus post-SING would be 0.01 arbitrary units and the within-patient standard deviation of the parameter estimates would be 0.02. We will analyze the model parameter specific to each of the four interventions in a 2x2 design (Activity vs Ownership) using Analysis of Variance, leveraging the added power of within-participants designs. We estimate we will need at least 31 participants to have 80% power to detect a treatment difference at a two-sided 0.05 significance level⁵⁴. We budgeted for 50 unique participants per group to allow for participant drop-out and the detection of smaller effects of SING on conditioned hallucination behavior, social learning and language use.

Robustness and reproducibility (both phases). We have built in a replication study of the effects of SING on conditioned hallucinations, social learning and language use across our R61 and R33 studies (should those metrics satisfy our Go/No-Go criteria). We have chosen to focus on metrics with face and construct validity for psychosis, whose implication in the mechanisms of psychosis have been conceptually replicated across labs in different cities⁵⁷ and countries⁵⁸. Our tasks, analysis code, and data will be made freely available via Yale's ModelDB site. We will optimize and manualize the SING and control interventions in order to prosecute the R61 and R33. Those manuals will be available open access also.

SECTION II: RESEARCH INVOLVING DRUGS, BIOLOGICS, RADIOTRACERS, PLACEBOS AND DEVICES

If this section (or one of its parts, A or B) is not applicable, check off N/A and delete the rest of the section.

- A. RADIOTRACERS N/A
- B. DRUGS/BIOLOGICS N/A
- C. DEVICES N/A

SECTION III: RECRUITMENT/CONSENT AND ASSENT PROCEDURES

1. Targeted Enrollment: *Give the number of subjects.*

- a. Targeted for enrollment at Yale for this protocol: R61, n = 50. R33, n = 200. Total n = 250.
- b. If this is a multi-site study, give the total number of subjects targeted across all sites: N/A

2. Indicate recruitment methods below. *Attach copies of any recruitment materials that will be used.*

- | | | |
|--|---|---|
|  Flyers |  Internet/web postings |  Radio |
|  Posters |  Mass email solicitation |  Telephone |
|  Letter |  Departmental/Center website |  Television |
|  Medical record review* |  Departmental/Center research boards |  Newspaper |
|  Departmental/Center newsletters |  Web-based clinical trial registries |  Clinicaltrials.gov |
|  YCCI Recruitment database |  Social Media (Twitter/Facebook): | |
|  Other: | | |

* Requests for medical records should be made through JDAT as described at <http://medicine.yale.edu/ycci/oncore/availableservices/datarequests/datarequests.aspx>

3. Recruitment Procedures:

- a. *Describe how potential subjects will be identified.*

Potential participants will self-identify in response to our recruitment materials. Potential participants may also be referred by the Specialized Treatment Early in Psychosis (STEP) program.

- b. *Describe how potential subjects are contacted.*

Potential participants will contact us through call/text/email. If referred to us, we will contact potential participants through call/text/email. We will be contacting participants via our study email address ([contact]), our Yale study cellphone, or office phone.

- c. *Who is recruiting potential subjects?*

[name] and his team will recruit participants.

4. Assessment of Current Health Provider Relationship for HIPAA Consideration:

Does the Investigator or any member of the research team have a direct existing clinical relationship with any potential subject?

- Yes, all subjects
 Yes, some of the subjects
 No

5. **Request for waiver of HIPAA authorization:** *(When requesting a waiver of HIPAA Authorization for either the entire study, or for recruitment purposes only. Note: if you are collecting PHI as part of a phone or email screen, you must request a HIPAA waiver for recruitment purposes.)*

Choose one:

- For entire study
- For recruitment/screening purposes only
- For inclusion of non-English speaking subject if short form is being used and there is no translated HIPAA research authorization form available on the University's HIPAA website at hipaa.yale.edu.

- i. *Describe why it would be impracticable to obtain the subject's authorization for use/disclosure of this data: We would like to talk to all potential participants by telephone prior to their screening visit (and their signing consent) to confirm eligibility, interest, and ability to commit to the study.*

Participants will contact us or will be contacted for a phone screen prior to being invited in for the informed consent and in-person screening session.

- ii. *If requesting a waiver of **signed** authorization, describe why it would be impracticable to obtain the subject's signed authorization for use/disclosure of this data: Since their first point of contact with the study will be telephone.*

It would be impossible to provide signed consent prior to a telephone screen that allows us to discern whether to see someone in person for a screening session.

The investigator assures that the protected health information for which a Waiver of Authorization has been requested will not be reused or disclosed to any person or entity other than those listed in this application, except as required by law, for authorized oversight of this research study, or as specifically approved for use in another study by an IRB.

Researchers are reminded that unauthorized disclosures of PHI to individuals outside of the Yale HIPAA-Covered entity must be accounted for in the "accounting for disclosures log", by subject name, purpose, date, recipients, and a description of information provided. Logs are to be forwarded to the Deputy HIPAA Privacy Officer.

6. **Process of Consent/Assent:** *Describe the setting and conditions under which consent/assent will be obtained, including parental permission or surrogate permission and the steps taken to ensure participants' independent decision-making.*

After phone screen, eligible participants will be invited to come to the CMHC for consent. A member of the research team will describe the study to potential participants, provide those who are interested with a consent form to read, answer all questions, and then obtain oral and written consent before beginning any study. Participants who wish to take the form home to consider it further before providing consent will have the option to do so. They may call study staff later to arrange a follow-up visit if they wish to consent to the study and continue the full clinical characterization. Otherwise, this may be completed at time of consent.

It is possible that some people with schizophrenia will have a conservator. They may wish to participate. In this case we will seek the person's assent and that of their conservator (by adding an optional conservator

signature on the document). We will also ensure that they understand the procedure and their relationships with the study team and their clinical team (that they are different). Since the conservator will need to sign the document too, this will ensure that there is an extended decision period for conserved persons. We will also arrange, with the person's assent, for [name] or one of the study team members to speak with the conservator before the person is randomized to the study.

7. **Evaluation of Subject(s) Capacity to Provide Informed Consent/Assent:** *Indicate how the personnel obtaining consent will assess the potential participant's ability and capacity to consent to the research being proposed. A member of study personnel will complete an in-person clinical assessment at intake. This assessment will include questions about the study procedures and possible risks to ensure the participant understands the study and is making an informed decision.*
8. **Non-English Speaking Subjects:** *Explain provisions in place to ensure comprehension for research involving non-English speaking participants. If enrollment of these participants is anticipated, translated copies of all consent materials must be submitted for approval prior to use.*

We will not recruit non-English speaking participants, they must be fluent in English to participate.

Note* If more than 2 study participants are enrolled using a short form translated into the same language, then the full consent form should be translated into that language for use the next time a subject speaking that language is to be enrolled.

Several translated short form templates are available on the HRPP website (yale.edu/hrpp) and translated HIPAA Research Authorization Forms are available on the HIPAA website (hipaa.yale.edu). If the translation of the short form is not available on our website, then the translated short form needs to be submitted to the IRB office for approval via modification prior to enrolling the subject. ***Please review the guidance and presentation on use of the short form available on the HRPP website.***

If using a short form without a translated HIPAA Research Authorization Form, please request a HIPAA waiver in the section above.

9. **Consent Waiver:** *In certain circumstances, the HIC may grant a waiver of signed consent, or a full waiver of consent, depending on the study. If you will request either a waiver of consent, or a waiver of signed consent for this study, complete the appropriate section below.*

Not Requesting any consent waivers

Requesting a waiver of signed consent:

Recruitment/Screening only *(if for recruitment, the questions in the box below will apply to recruitment activities only)*

Entire Study *(Note that an information sheet may be required.)*

For a waiver of signed consent, address the following:

- *Would the signed consent form be the only record linking the subject and the research?* YES NO
- *Does a breach of confidentiality constitute the principal risk to subjects?* YES NO

OR

- *Does the research pose greater than minimal risk?* YES NO
- *Does the research include any activities that would require signed consent in a non-research context?*
YES NO

 Requesting a waiver of consent:

Recruitment/Screening only (if for recruitment, the questions in the box below will apply to recruitment activities only)

Entire Study

For a full waiver of consent, please address all of the following:

- *Does the research pose greater than minimal risk to subjects?*
 - Yes - If you answered yes, stop. A waiver cannot be granted.**
 - No**
- *Will the waiver adversely affect subjects' rights and welfare?* YES NO
- *Why would the research be impracticable to conduct without the waiver?*
- *Where appropriate, how will pertinent information be returned to, or shared with subjects at a later date?*

SECTION IV: PROTECTION OF RESEARCH SUBJECTS
--

Confidentiality & Security of Data:

1. *What protected health information (medical information along with the HIPAA identifiers) about participants will be collected and used for the research?*

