Participant recruitment and screening. The Connecticut Mental Health Center has specialty clinics for first episode and multi-episode patients that will serve as primary recruitment sites. People who pass an initial phone screen will be invited to an in-person screening which includes a review of medical history, the SCID³², and Structured Interview for DSM Personality Disorders – Revised (SIDP-R)³³. To ensure adequate variability in positive symptom severity and balance in the clinical groups (R33 Phase), we will review ratings of hallucinations, assessed using the BPRS³⁴, during the initial study visit. We aim to include participants with at least a score >3 on the hallucinations item.

Participants will be between the ages of 18-65. Exclusion of older subjects is based on concern for effects of aging on behavioral parameters. Subjects of any gender and any race/ethnicity will be recruited to ensure the recruited group closely approximates the racial/ethnic base-rates in New Haven.

Assessments and Questionnaires

Self-report measures. The Launay-Slade Hallucinations Scale provides a brief measure of hallucinatory experience. They need to have experienced hallucinations at least once a day. Subjects' distress associated with their experiences will also be assessed and used in our analyses, as we and others have found that it clinically relevant³⁵. The Positive and Negative Affect Scale (PANAS³⁶) will be used to provide an assessment of current affective state.

Standard Neuropsychological Measures. We will administer the Wechsler Test of Adult Reading (WTAR)³⁷ as a measure of premorbid intellectual ability, and the MATRICS³⁸ Battery to assess level of neuropsychological functioning. Correlations between these measures, task metrics and the effects of MI will reveal the degree to which the metrics we acquire (and how they change with MI) are mechanistically specific.

Experimental Procedures and Anticipated Results

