R61 Aim 2 – Social Learning: Participants will play the social valuation task pre- and post-SING. As described above, this is a reinforcement learning task with distinct periods of high and low volatility. It is 120 trials long. For the first 40 trials, social volatility is low. For the remaining 80 trials, social volatility is high. The task also includes a non-social cue (green vs blue color) on each trial. Periods of volatility for the non-social cue are designed to be orthogonal to those for the social cue: this allows us to compare responses to both social and non-social cues. Participants will meet a gender-matched confederate for a brief interaction. Lab staff will review the task instructions with the subject and confederate together. The instructions include the information that the confederate's advice may be helpful or unhelpful because the confederate is responding to a separate reward scheme. The participant will complete a practice task to ensure that the instructions are clear. The participant will then watch the confederate complete a practice task. Having the participant watch the confederate practice helps to facilitate the fiction that the confederate is a real participant who needs to learn the task, and allows the participant to see the confederate make both helpful and unhelpful choices. We will use participant behavior to estimate prior expectations for volatility and prediction errors using the Hierarchical Gaussian Filter approach described above and previously employed with this task²⁶⁻²⁸. As above, parallel versions of the social valuation task with a different confederate and different card deck colors will be employed. **We predict** learning rates will be blunted under social volatility in people with AVH, and that this effect will normalize with SING

R61 Aim 3 - Qualitative Interviews: Participants will complete in-depth interviews both before and upon completion of SING. Interviews will focus on their previous experience with music, their experience of participating in the group intervention (post-intervention interview only), and their sense of self in three domains (narrative, embodied, intersubjective) related to the predictive processing theory of voices, psychosis and self.

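### The social task includes a non-social cue for comparison, but no Aim 2 prediction, test or R33 model uses it, so a general change in learning could be reported as a social one.

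*Combined protocol and SAP*

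**What the plan says.** Section I, item 4, R61 Aim 2 – Social Learning, describes a 120-trial task played before and after SING. On the social side, "For the first 40 trials, social volatility is low. For the remaining 80 trials, social volatility is high". The section adds: "The task also includes a non-social cue (green vs blue color) on each trial". It then says "Periods of volatility for the non-social cue are designed to be orthogonal to those for the social cue", and gives the purpose: "this allows us to compare responses to both social and non-social cues". Retesting uses parallel versions with another confederate and other deck colours.

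The prediction that closes the section is that "learning rates will be blunted under social volatility in people with AVH, and that this effect will normalize with SING". It has no non-social term.

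In Section I, item 13, R61 Statistical Power states: "We will analyze the model parameter specific to each Aim using paired sample's t-tests". The Go/No Go Decision takes a metric forward if "Conditioned Hallucination parameters, social learning rates or use of personal pronouns, biological words or negative emotional words change by two standard deviations or more" from its pre-intervention level. R33 Power to Detect Effects plans a 2x2 analysis of variance (Activity, Ownership) with no cue factor.

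Specificity is addressed in one other place. Under Standard Neuropsychological Measures (item 4), correlations of the WTAR and MATRICS with the task metrics and the effects of the intervention "will reveal the degree to which the metrics we acquire (and how they change with MI) are mechanistically specific".

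**The concern.** Aim 2 makes a claim about social learning. A pre-post rise in a social learning rate could come from better social learning. It could also come from better learning in general, better attention, or familiarity with the task at the second visit. R61 has no comparison arm to remove the general explanations. The plan's own background (item 3, Music and Psychosis) cites a meta-analysis in which music interventions helped cognitive as well as negative symptoms, so general change is a plausible rival. It is weak evidence about learning rates, because the same paragraph says those outcomes were subjective ratings.

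The colour cue gives each participant a matched non-social measure at each visit. Without a planned use for it, the Aim 2 conclusion rests on a test that gives the same answer whether the change is social or general.

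**Working it through.** **1. The plan's own figure.** R61 Statistical Power uses a difference of 0.01, an SD of 0.02, two-sided 0.05 and 80% power, and states 31 participants. Reading 0.02 as the SD of the paired difference:

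n = (0.02 × (1.960 + 0.842) / 0.01)² = 31.4

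This reproduces 31 (rounded down). An exact paired t calculation gives 34, with 76.8% power at 31. These inputs belong to the conditioned-hallucination parameter. The documents give no effect or SD for social learning rates, so the steps below work in SD of change or borrow the 0.01/0.02 pair as an assumption.

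**2. A shift common to both cues and no social effect.** Let g be the shift in SD-of-change units, assumed equal on both cues. The social-only paired t-test has noncentrality g√n. At n = 50, √n = 7.07.

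| g (assumed) | g√50 | P(p<0.05), social-only, n = 50 | same, n = 31 | contrast |
|---|---|---|---|---|
| 0.125 | 0.88 | 14% | 10% | 5% |
| 0.25 | 1.77 | 41% | 27% | 5% |
| 0.30 | 2.12 | 55% | – | 5% |

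The contrast is the social change minus the non-social change. Its mean is zero when the shift is equal on both cues, so its error rate stays at 5%.

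**3. The Go rule.** The bar is two SD. On a group-mean reading, and assuming the SD of change is about the baseline SD, the standard error at n = 50 is 1/√50 = 0.14 SD. A shift of 0.30 SD then lies (2 − 0.30)/0.14 ≈ 12 standard errors below the bar. The step 2 figures concern the t-test alone.

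**4. The cognitive correlations.** The CI half-width at an observed r of 0 and n = 50 is tanh(1.96/√47) = 0.28, so the interval runs from about −0.28 to 0.28. The correlation detectable with 80% power is tanh(2.80/√47) = 0.39. The WTAR is described as a measure of premorbid ability, and no section schedules the MATRICS after SING. A near-zero correlation therefore leaves moderate associations open and does not track cognitive change.

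**5. What the contrast costs in power.** With equal SDs and correlation r between the two changes, the contrast SD is 0.02 × √(2(1 − r)). Suppose the borrowed 0.01 effect is wholly social:

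| r (assumed) | contrast SD | effect/SD | power at n = 50 | n for 80% power (exact t) |
|---|---|---|---|---|
| 0 | 0.0283 | 0.35 | 69% | 65 |
| 0.25 | 0.0245 | 0.41 | 81% | 50 |
| 0.5 | 0.0200 | 0.50 | 93% | 34 |
| 0.75 | 0.0141 | 0.71 | >99% | 18 |

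Below r = 0.5 the contrast is less precise than the social-only test, and above it more precise.

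**6. If SING acts on both cues.** Suppose half the effect reaches the non-social cue and r = 0.5. The contrast is 0.01 − 0.005 = 0.005 with SD 0.02, an effect of 0.25 SD, and power at n = 50 is 41%.

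**The case against.** The protocol does not ignore the cue. It says the cue permits a comparison, and other safeguards exist.

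- Parallel versions limit item-specific practice. They do not remove familiarity with the procedure, better attention or better general learning.
- The low-versus-high social volatility comparison is a second within-person control, and an additive general shift cancels in it. But its order is fixed, so it is confounded with time on task, and it cannot separate learning about social volatility from learning about volatility in general.
- R33 randomises to four arms that are tested alike. Retest effects common to all arms drop out of the Activity and Ownership comparisons. What remains open there is narrower: whether an arm difference is specifically social.

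A reader might infer that the Go rule would readily pass a small general shift. Step 3 does not support that. The rule cannot tell a large general change from a large social one, but a shift of a few tenths of an SD is very unlikely to reach it on the group-mean reading.

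A reader might also conclude that Go should be conditional on the contrast. The plan's theory argues against this. Item 3, Music & Predictive Processing, and the R33 rationale in item 4 allow effects at levels of processing not tied to one modality. Such effects could reach both cues, and subtraction would remove part of a real effect (step 6).

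Finally, the shift sizes in step 2 have no source in the documents. They show how the test behaves and do not predict this trial.

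**Conclusion.** The point holds as a gap in prespecification. The non-social cue is collected and its purpose is stated, but the Aim 2 prediction, the R61 test, the Go rule and the R33 model give it no role. In single-arm R61, a significant social-only result cannot be attributed to social learning specifically, and the cognitive correlations cannot supply that attribution at n = 50.

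The size depends on an unknown general shift: 14% to 55% false social findings for assumed shifts of 0.125 to 0.30 SD of change with 50 completers, against 5% for the contrast. This assumes the shift is equal on both cues and passes undiminished into the tested metric. A metric built as high-minus-low social volatility would absorb some of it. The documents do not support the stronger readings that the Go decision is exposed to small shifts, or that R33 arm comparisons carry common practice effects. This is an inexpensive improvement to what Aim 2 can conclude.

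**What to change.** 1. In R61 Aim 2 and R61 Statistical Power, prespecify, alongside the social-only test, the contrast (post minus pre change in the social metric) minus (post minus pre change in the matched non-social metric). Analyse it by paired t-test and report it with a 95% CI. Define the matched metric as the same model parameter for the colour cue, and state the colour cue's low- and high-volatility trial ranges.
2. In the R33 analysis, add cue (social/non-social) as a within-person factor, so that its interaction with Activity and Ownership shows whether an arm difference is specifically social.
3. Leave the Go rule unchanged. Describe a change as specifically social only if the contrast supports it; otherwise describe it as a change in learning that may be general.
4. Under Standard Neuropsychological Measures, report the correlations with 95% CIs, and state that a non-significant one is not evidence of specificity.

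The cost is analysis wording only, because the cue is already part of the task. The contrast loses precision if the two changes correlate below 0.5, and it is attenuated if SING acts on both cues. The plan should state an assumed or pilot value for that correlation, since the power of the contrast depends on it.
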